COVID-19	Coronavirus disease 2019
CRF	Case Report/Record Form (paper or electronic)
CRO	Contract Research Organization
CSR	Clinical study report
CTC	Common Toxicity Criteria
CV	coefficient of variation
ECG	Electrocardiogram
EDC	Electronic Data Capture
ELISA	Enzyme-linked immunosorbent assay
EoS	End of Study
EoT	End of Treatment
eSAE	Electronic Serious Adverse Event
eSource	Electronic Source
FDA	Food and Drug Administration
FiH	First in human
FSH	Follicle Stimulating Hormone
GCP	Good Clinical Practice
GGT	Gamma-glutamyl transferase
h	hour
HbsAg	Hepatitis B surface antigen
HBV	Hepatitis B virus
HCV	Hepatitis C virus
HIV	human immunodeficiency virus
IB	Investigator's Brochure
ICF	Informed Consent Form
ICH	International Conference on Harmonization of Technical Requirements for Registration of Pharmaceuticals for Human Use
IEC	Independent Ethics Committee
IN	Investigator Notification
INR	International Normalized Ratio
IRB	Institutional Review Board
IRT	Interactive Response Technology
	1

LDH	lactate dehydrogenase
	Commercially Confidential Information
LTA4H	Leukotriene A4 hydrolase
LTB4	Leukotriene A4
LTC4	Leukotriene C4
LXA4	Lipoxin A4
MedDRA	Medical dictionary for regulatory activities
mg	milligram(s)
mL	milliliter(s)
PD	pharmacodynamic(s)
PhGA	Physician's global assessment

PT	prothrombin time	
Commercially Confidential Information		
QMS	Quality Management System	
QTcF	QT interval corrected by Fridericia's formula	
RBC	red blood cell(s)	
SAE	serious adverse event	
SAP	Statistical Analysis Plan	
sCR	serum creatinine	
SD	standard deviation	
Commercially Confidential Information		
SMQ	Standardized MedDRA Query	
SOM	Site Operations Manual	
SUSAR	Suspected Unexpected Serious Adverse Reactions	
TBL	Total bilirubin	
TNF	Tumor necrosis factor	
UC	Ulcerative colitis	
ULN	upper limit of normal	
Commercially Confidential Information		
WBC	white blood cell(s)	
WHO	World Health Organization	
WoC	Withdrawal of Consent	

Glossary of terms

Additional treatment	Medicinal products that may be used during the clinical trial as described in the protocol, but not as an investigational medicinal product (e.g. any background therapy)
Assessment	A procedure used to generate data required by the study
Biologic Samples	A biological specimen including, for example, blood (plasma, serum), saliva, tissue, urine, stool, etc. taken from a study subject
Cohort	A specific group of subjects fulfilling certain criteria
Control drug	A study drug (active or placebo) used as a comparator to reduce assessment bias, preserve blinding of investigational drug, assess internal study validity, and/or evaluate comparative effects of the investigational drug
Dosage	Dose of the study treatment given to the subject in a time unit (e.g. 100 mg once a day, 75 mg twice a day)
Electronic Data Capture (EDC)	Electronic data capture (EDC) is the electronic acquisition of clinical study data using data collection systems, such as Web-based applications, interactive voice response systems and clinical laboratory interfaces.
	EDC includes the use of Electronic Case Report Forms (eCRFs) which are used to capture data transcribed from paper source forms used at the point of care.
End of the clinical trial	The end of the clinical trial is defined as the last visit of the last subject or at a later point in time as defined by the protocol
Enrollment	Point/time of subject entry into the study at which informed consent must be obtained (i.e. prior to starting any of the procedures described in the protocol)
eSource	eSource Direct Data Entry (DDE) refers to the capture of clinical study data electronically, at the point of care. eSource combines source documents and case report forms (eCRFs) into one application, allowing for the real time collection of clinical trial information to sponsors and other oversight authorities, as appropriate.
Healthy volunteer	A person with no known significant health problems who volunteers to be a study participant
Investigational drug/treatment	The drug whose properties are being tested in the study
Medication pack number	A unique identifier on the label of each drug package in studies that dispense study treatment using an IRT system
Part	A single component of a study which contains different objectives or populations within that single study. Common parts within a study are: a single dose part and a multiple dose part, or a part in patients with established disease and in those with newly-diagnosed disease.
Patient	An individual with the condition of interest
Personal Data	Subject information collected by the Investigator that is transferred to Novartis for the purpose of the clinical trial. This data includes subject identifier information, study information and biological samples
Randomization number	A unique identifier assigned to each randomized subject, corresponding to a specific treatment arm assignment
Screen Failure	A subject who is screened but is not treated or randomized
Source Data/Document	Source data refers to the initial record, document, or primary location from where data comes. The data source can be a database, a dataset, a spreadsheet or even hard-coded data, such as paper or eSource

Study treatment	Any drug or combination of drugs administered to the study participants as part of the required study procedures; includes investigational drug(s), control(s) or background therapy
Study treatment discontinuation	When the subject permanently stops taking study treatment prior to the defined study treatment completion date
Subject	A trial participant (can be a healthy volunteer or a patient)
Subject number	A unique number assigned to each subject upon signing the informed consent. This number is the definitive, unique identifier for the subject and should be used to identify the subject throughout the study for all data collected, sample labels, etc.
Treatment number	A unique identifier assigned in non-randomized studies to each dosed subject, corresponding to a specific treatment arm
Variable	A measured value or assessed response that is determined in specific assessments and used in data analysis to evaluate the drug being tested in the study
Withdrawal of consent (WoC)	Withdrawal of consent from the study occurs only when a subject does not want to participate in the study any longer, and does not allow any further collection of personal date

Protocol summary

Protocol number	LYS006X2202
Full Title	A randomized, multi-center, subject and investigator blinded, placebo controlled, parallel group study to assess the efficacy, safety and tolerability of LYS006 in patients with mild to moderate ulcerative colitis.
Brief title	Study of efficacy, safety and tolerability of LYS006 in patients with mild to moderate ulcerative colitis
Sponsor and	Novartis
Clinical Phase	Phase II
Investigation type	Drug
Study type	Interventional
Purpose and rationale	The purpose of the study is to assess preliminary efficacy, safety and tolerability of LYS006 in patients with mild to moderate ulcerative colitis and to determine if LYS006 has an adequate clinical profile for further clinical development in this indication.
Primary Objective(s)	To assess the induction of clinical remission by LYS006 in patients with mild to moderate ulcerative colitis using the full Mayo score.
Secondary Objectives	To assess safety and tolerability of LYS006 in patients with mild to moderate ulcerative colitis
Study design	This is a randomized, placebo-controlled, subject and investigator blinded, multicenter, non-confirmatory, parallel group, proof of concept study in patients with mild to moderate ulcerative colitis. This study consists of a screening period of up to 4 weeks (minimum one week), an 8-week treatment period followed by a 30-day post treatment period safety follow up. The maximum study duration for each such including the maximum 4-week screening period is 16 weeks.
	At the beginning of the treatment period, subjects will be randomized to one of the two following treatment groups in 2:1 ratio: 20 mg LYS006 (BID) matching placebo (BID)
Population	This study will include patients with mild to moderate ulcerative colitis who failed an appropriate, previous treatment with 5-ASA. These patients should have active disease defined as having a full Mayo Score between 5 and 10 (inclusive), with baseline endoscopic sub score of 2 or 3; rectal bleeding and stool frequency score of 1 to 3 and physician's global assessment 1 or 2. Approximately 45 subjects are planned to be enrolled.
Key Inclusion criteria	 Male and female subjects 18-75 years of age with an established diagnosis of ulcerative colitis at least 3 months prior to screening are eligible for the study. Patients must have active disease with a full Mayo Score between 5 and 10 (inclusive) with an endoscopy score of 2 or 3; rectal bleeding and stool frequency scores 1 to 3 and a physician's global assessment with a maximum of 1 or 2.
	Patients must have responded inadequately to conventional therapy with oral 5-ASA prior to screening.

Key Exclusion criteria	 Has severe UC at screening, as defined by ≥6 bloody stools per day and at least one of the following:
	Pulse >90 bpm
	Oral temperature of >37.8°C
	Hemoglobin of <10.5 g/dL
	• CRP > 30 mg/L
	 Erythrocyte sedimentation rate (ESR) >30 mm/h
	 Has previous diagnosis with Crohn's disease, indeterminate colitis, microscopic colitis or acute diverticulitis based on medical history.
	 Previous treatment with biologics (such as anti-TNFα agents) within 3 months or 5 half-lives (whichever is longer) prior to screening endoscopy
	 Previous treatment with non-biologics (such as JAK inhibitors) within 4 weeks prior to screening endoscopy
	 Any systemic immunosuppressant or immunomodulator, such as cyclosporine, methotrexate, azathioprine within 6 weeks and cyclophosphamide within 3 months, prior to screening endoscopy
	 A dose of > 10 mg/d prednisone or equivalent in the last 4 weeks prior to screening endoscopy. Oral budesonide is allowed if the dose is ≤ 9 mg/day with a stable dose administered for at least 4 weeks prior to the screening endoscopy.
Study treatment	LYS006 20 mg BID: 8 weeks
oracy arounders	Matching placebo BID: 8 weeks
Key Efficacy	Mayo Score based on:
assessments	Stool frequency
	Rectal bleeding
	Endoscopic findings
	Physician's Global Assessment
Other assessments	Commercially Confidential Information
Key safety	AE, SAE monitoring
assessments	Physical examinations
	Monitoring of laboratory safety
	• ECGs
	Vital signs
Data analysis	The primary endpoint of this study is the clinical remission rate at End of treatment (EoT) CCI and Week 8 for subsequent protocol amendments), i.e. the proportion of patients reaching the status of clinical remission. This primary endpoint of clinical remission is based on full Mayo score, defined as a Mayo score ≤2 with no individual subscore >1. Patients who discontinue for reasons other than COVID-19, or receive any rescue medication before EoT will be considered as treatment failure. This binary endpoint will be analyzed with a Bayesian approach, to compare the remission rates between LYS006 and placebo group. An informative prior will be used for the remission rate for placebo (refer to Sample Size section for details) and a neutral prior (Kerman 2011), Beta (1/3, 1/3), for LYS006. The posterior probabilities as defined in the dual efficacy criteria detailed in the

	analysis of the primary endpoint section will be provided, along with the posterior remission rates by group and the treatment difference with 90% credible intervals.
Key words	Ulcerative colitis, efficacy, safety

Protocol No. CLYS006X2202

1 Introduction

1.1 Background

Ulcerative colitis (UC) is a common chronic immune-mediated disorder that results in inflammation and ulcers in the gastrointestinal tract, and leads to symptoms such as diarrhea, abdominal pain and rectal bleeding. Although 5-ASA compounds as first line agents have been proven safe and are used extensively in UC, there is a significant proportion of patients with inadequate responses due to insufficient therapeutic response or toxicity.

During relapse, UC is characterized by acute neutrophilic inflammation accompanied by considerably enhanced mucosal levels of inflammatory lipidic mediators including Leukotriene B4 (LTB4). LTB4 is a potent neutrophil chemoattractant and chemoactivator. Functional studies have established that LTB4 accounts for the majority of the chemoattractant stimulus to continuing neutrophil infiltration found during relapse (Sharon and Stenson 1984; Cole et al 1992). 5-Lipoxygenase (5-LO, upstream to LTA4H) inhibitor Zileuton indicates clinical benefit of inhibiting LTB4 release in ulcerative colitis (Peppercorn et al 1994). LTA4H inhibition is expected to lead to better efficacy than 5-LO inhibition due to more complete pathway inhibition and simultaneous elevation of LXA4 (maintenance of resolution lipids), a mediator that has been found to be elevated during the remission period in UC patients (Vong et al 2012).

Therefore, LYS006, a potent LTA4H inhibitor that abrogates the production of LTB4 and triggers elevation of pro-resolution mediators such as LXA4, may be beneficial to subjects with ulcerative colitis.

Commercially Confidential Information

Additionally, LTA4H inhibition improves colitis in rats /cotton top tamarins (Whittle et al 2008; Penning 2001). These preclinical findings suggest that using LYS006 to target neutrophilic inflammation through the leukotriene pathway may be a therapeutic option for UC, in particular for subjects with active UC who have failed first line therapy with 5-ASA and for whom no safe treatment or combination of medical treatments has proven fully efficacious and/or safe and the unmet medical need is still high.

The most relevant data on LYS006 are summarized in the sections below. For detailed information, please refer to the Investigator's Brochure (IB).

Relevant data summary

In parallel to the proposed Phase 2 study in UC, LYS006 is being evaluated in inflammatory acne, hidradenitis suppurativa and nonalcoholic steatohepatitis (all phase 2 studies).

1.2 **Purpose**

Novartis

The study is designed to assess clinical efficacy and safety of LYS006 in adult patients with mild to moderate ulcerative colitis.

2 **Objectives and endpoints**

[figure not shown]
Table 2-1 Objectives and related endpoints

Objective(s)	Endpoint(s)
Primary objective(s)	Endpoint(s) for primary objective(s)
 To assess the induction of clinical remission by LYS006 in patients with mild to moderate ulcerative colitis compared to placebo 	 Clinical remission rate at week 8 using the full Mayo score (see Section 12.4.1 for more details)
Secondary objective(s)	Endpoint(s) for secondary objective(s)
 To assess safety and tolerability of LYS006 in patients with mild to moderate ulcerative colitis compared to placebo 	 Number and severity of adverse events / number of subjects with adverse events
	 Safety and tolerability based on general safety measurements (safety laboratory parameters, vital signs and ECG parameters)

3 Study design

This is a randomized, placebo-controlled, subject and investigator blinded, multicenter, parallel group study in patients with mild to moderate ulcerative colitis. Each individual subject will first undergo a screening period of up to 4 weeks (minimum screening duration of 7 days to enable collection of stool frequency and rectal bleeding subscores), a treatment period of 8 weeks and a follow-up period of 30 days post last administration of study treatment, before the End of Study visit. The total duration for each subject in the study will be up to 16 weeks. See Figure 3-1.

Figure 3-1 Study design

Approximately 45 subjects will be randomized in a 2:1 ratio to one of the following treatment groups:

- Group 1: LYS006 capsules (20 mg BID)
- Group 2: matching placebo (BID)

For the entire duration of the treatment period (8 weeks), subjects will receive twice-daily doses of LYS006 or placebo, so that the blind is maintained throughout the entire study. For further details, please refer to Section 6.

Safety assessments will include physical examination, ECGs, vital signs, standard clinical laboratory evaluations (hematology, biochemistry and urinalysis) as well as adverse event and serious adverse event monitoring.

Commercially Confidential Information

Screening

After signing informed consent, screening evaluations will take place from Day -28 to Day -1 (minimum screening duration of 7 days to enable collection of stool frequency and rectal bleeding subscores). During that period all safety and other assessments must be performed to evaluate eligibility. The endoscopy* is to be performed between Day -7 and Day -4 before the planned baseline visit. (Table 8-1).

*A colonoscopy is required if the patient has no documented colonoscopy within the preceding 12 months. All other subjects can have a sigmoidoscopy performed at screening.

Subjects will be provided with the paper diaries to record data on stool frequency and rectal bleeding parameters on a daily basis until the end of the study. In addition, study medication intake data will also be recorded by the subject for compliance reasons.

Subjects that fail screening, may be re-screened on one further occasion after discussion and agreement with the sponsor on a case by case basis.

Baseline

Eligible subjects will return for the Baseline visit on Day 1. Eligibility must be confirmed prior to randomization and required baseline assessments must be completed prior to dosing on Day 1.

Treatment

Subjects will be randomized to the respective treatment arm using a centralized Interactive Response Technology (IRT) system at the completion of Baseline visit, after eligibility is confirmed. Subjects will receive their morning dose of LYS006 or placebo at the site on Days 1, 29 and 57, CCI , once all pre-dose assessments have been completed. Subjects will then be provided study drug and may return home to continue their daily dosing regimen (self-administration).

Commercially Confidential Information

At all study visits, subjects will undergo safety and efficacy assessments, as indicated in the Assessment Schedule and described in Section 8.

At all visits CCI subjects will return their used drug supply kits for compliance and accountability assessment Commercially Confidential Information

Subjects' diary data on stool frequency and rectal bleeding parameters will be checked by site personnel on visit days for efficacy assessment. Commercially Confidential Information

Subjects will be contacted by the Investigator/site staff during the study to ensure compliance/monitor safety by telephone or other means, if it is deemed appropriate or necessary by the Investigator.

Commercially Confidential Information

Follow up and End of Study visit (EoS)

After the last day of dosing (EoT), and all safety and efficacy assessments are completed, all subjects will enter a 30-day Post-Treatment Follow Up period without study drug administration. Subjects will then be asked to return to the site at Day 87 for the End of Study visit. At this visit, subjects will undergo final assessments as indicated in the Assessment schedule (Table 8-1). Upon completion of this visit, subjects will be discharged from the study.

4 Rationale

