5.1 Inclusion criteria

Subjects eligible for inclusion in this study must meet all of the following criteria:

- 1. Written informed consent must be obtained before any assessment is performed.
- 2. Male and female subjects aged 18-75 years at screening
- 3. Patients diagnosed with UC established at least 3 months prior to screening.
- 4. Patients with mild to moderate UC which is defined by a total Mayo Score between 5 and 10 (inclusive), comprised of the following subscores;
 - Endoscopic subscore: 2 or 3 (determined from central reading of screening endoscopy)
 - Stool frequency subscore: 1-3

- Rectal bleeding subscore: 1-3
- Physician's global assessment subscore: 1-2. Please see the SOM for guidance on completion of Mayo scores
- 5. Disease must extend beyond 15 cm from the anal verge (assessed by screening endoscopy).
- 6. Patients must have responded inadequately or have intolerance to conventional therapy with oral 5-ASA prior to screening, and be willing to continue 5-ASA at a stable dose during the study treatment period. Inadequate response is defined by the following:
 - Active disease despite induction therapy with 5-ASA agents where adequate therapy is a stable oral 5-ASA dose.
 - Adequate therapy is an oral 5-ASA (mesalamine ≤ 4.8 g/day, sulfasalazine ≤ 6 g/day, balsalazide ≤ 7.5 g/day or olsalazine ≤ 3 g/day) with a stable dose administered for at least 4 weeks prior to the screening endoscopy.
 - In addition to oral 5-ASA, oral corticosteroids including oral budesonide are permitted provided the following criteria are met and the patient is willing to continue to continue the medication at a stable dose during the study treatment period
 - o Oral corticosteroids are allowed if the dose is < 10 mg/day with a stable dose administered for at least 4 weeks prior to the screening endoscopy.
 - Oral budesonide is allowed if the dose is $\leq 9 \text{ mg/day}$ with a stable dose administered for at least 4 weeks prior to the screening endoscopy.
- 7. Able to communicate well with the investigator, to understand and comply with the requirements of the study.

5.2 **Exclusion criteria**

Subjects meeting any of the following criteria are not eligible for inclusion in this study.

- 1. Use of investigational drugs within 4 weeks or 5 half-lives of screening, whichever is longer; or longer if required by local regulations.
- 2. Confirmed laboratory findings at screening showing:

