8.3.1.1 Subject diary: Stool frequency and Rectal bleeding

Stool frequency and rectal bleeding are the main clinical symptoms of ulcerative colitis. Calculation of the Mayo score requires an assessment of stool frequency and rectal bleeding. Data on these clinical symptoms will be recorded by subjects on a daily basis using a paper diary until the end of the treatment period. Subjects will be provided with instructions on how to complete the paper diary at the screening visit. These should be reviewed at each visit until EoT by site staff, with retraining provided to subjects if the diaries are not completed correctly.

See the Site Operations Manual for guidance on training the subjects in the use of the diary and using the diary data to complete the Mayo score.

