8.3.1.2 Endoscopy

Assessment of clinical efficacy through longitudinal (repeated) endoscopic examination provides an objective readout and decreases the risk of having false positive results (based on clinical symptoms only). Endoscopy is the best means for assessment of extent and severity of colon mucosal inflammation.

Type of endoscopy

A screening colonoscopy is required if the patient has no documented colonoscopy within the preceding 12 months. If a documented report of colonoscopy performed within the 12 months preceding screening is available in the source notes, the patient can have a sigmoidoscopy performed at screening.

Sigmoidoscopies will be performed at all other visits.

The colonoscopy will require a bowel preparation with drinking a liquid that will trigger bowelclearing diarrhea and will be performed with adequate sedation as per local clinical practice. The sigmoidoscopy will require enemas before the procedure to clean out the lower part of the colon.

The endoscopic report (historical colonoscopy or screening endoscopy) must be available in the source documents.

Scheduling of endoscopies

Subjects should be seen for all visits/assessments as outlined, or as close to the designated day as possible. Missed or rescheduled visits should not lead to automatic discontinuation.

• Screening endoscopy: is to be performed between Day -7 and Day -4 before the baseline visit, to allow time to obtain endoscopic subscore report from the central read.

Note: The endoscopic subscore from central read will be used to determine eligibility.

Commercially Confidential Information

Endoscopic subscore

The mucosal appearance during the sigmoidoscopic portion of endoscopic examination will be assessed for the Mayo endoscopic subscore based on the scoring system provided in the Section 8.3.1. The endoscopic appearance will be read by the central reader through video recorded during the procedure. Centrally-read endoscopic sub-scores will be transferred to the Sponsor electronically. A report will be provided to the site for the screening score to be used for eligibility purposes.

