#### **6.1.1 Variables**

The primary PD variable of this study is the clinical remission rate at the EoT visit CCI, i.e. the proportion of patients who reach the status of clinical remission at the EoT visit.

Clinical remission is based on total Mayo score, defined as a total Mayo score of 2 points or lower, with no individual subscore exceeding one point. The total Mayo score is the sum of four subscores, ranging from 0 to 12: stool frequency (recorded on a daily basis by a diary card), rectal bleeding (recorded on a daily basis by a diary card), endoscopic findings and Physician's

Global Assessment (PhGA). Each subscore grading ranges from 0 to 3, from free of disease to severe disease.

The stool frequency subscore should be calculated from the most recent three consecutive days within the week prior to the day of endoscopy bowel preparation. If three consecutive days are not available, the most recent non-consecutive 3 days within the week prior to the day of endoscopy bowel preparation should be used. The stool frequency subscore is the average of the 3 daily stool frequency subscores. The rectal bleeding subscore will be calculated in the same manner as stool frequency subscore.

Commercially Confidential Information

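### Is the 7-day minimum screening too short to collect the diary days behind the screening Mayo subscores?

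*Protocol*

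**What the plan says.** Protocol Section 3 allows screening from Day -28 to Day -1, with a "minimum screening duration of 7 days to enable collection of stool frequency and rectal bleeding subscores". SAP 1.4 repeats this minimum. The baseline visit is on Day 1. The screening endoscopy "is to be performed between Day -7 and Day -4 before the planned baseline visit" (Section 3, Screening). Section 8.3.1.2 gives the reason for that window: it "is to be performed between Day -7 and Day -4 before the baseline visit, to allow time to obtain endoscopic subscore report" from the central reader.

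On the diary, Protocol 8.3.1.1 states: "Subjects will be provided with instructions on how to complete the paper diary at the screening visit". The same section refers sites to the Site Operations Manual for "using the diary data to complete the Mayo score". Inclusion criterion 4 in Protocol 5.1 also refers to that manual for completing Mayo scores.

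The only visible scoring window is in SAP 6.1.1: "The stool frequency subscore should be calculated from the most recent three consecutive days within the week prior to the day of endoscopy bowel preparation". The fallback there reads: "If three consecutive days are not available, the most recent non-consecutive 3 days within the week prior". Rectal bleeding is handled in the same way. This text sits under the primary variable, which is remission at the end-of-treatment (EoT) visit.

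**The concern.** The 7-day floor counts back from Day 1. The SAP 6.1.1 window counts back from bowel preparation, which comes at least four days before Day 1 because endoscopy can be no later than Day -4. Read together, the two leave little or no diary time for a patient screened at the minimum, although diary collection is the stated reason for that minimum. The SAP fallback does not help, because it still needs three days.

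The screening or baseline diary subscores have three visible uses:

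- eligibility (stool frequency and rectal bleeding each 1 to 3, total Mayo 5 to 10);
- descriptive change from baseline (SAP 6.1.2);
- the baseline total Mayo score named as an explanatory variable in SAP 6.1.3.

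If sites chose different diary days, baseline scores would not be built alike across about 45 patients.

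**Working it through.** The plan gives no derivation of the seven days, so there is no figure to reproduce. The check is a count of days.

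**Inputs.** From the documents: screening starts on Day -7 at the minimum, endoscopy day E is -7, -6, -5 or -4, and three diary days are needed before preparation day P. Assumed, because the visible text does not say: P is E or E - 1, the first diary day F is the screening day or the next day, and there is no Day 0.

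**Formula.** Usable diary days = max(0, P - F).

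**If the SAP 6.1.1 window applied at screening, with a Day -7 start:**

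| Preparation | First entry | E = -7 | E = -6 | E = -5 | E = -4 |
|---|---|---|---|---|---|
| Same day | Day -7 | 0 | 1 | 2 | 3 |
| Same day | Day -6 | 0 | 0 | 1 | 2 |
| Day before | Day -7 | cannot occur | 0 | 1 | 2 |
| Day before | Day -6 | cannot occur | 0 | 0 | 1 |

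The two excluded cells put preparation on Day -8, before screening has started. Of the remaining 16 - 2 = 14 schedules, one gives three days: -4 - (-7) = 3. It has no room for a missed entry. These are counts of schedules, not probabilities.

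**Screening length needed under that window.** Shortest length = 3 + |P|, plus 1 if the first entry is made the day after screening starts.

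- Endoscopy on Day -4: from 3 + 4 = 7 to 3 + 5 + 1 = 9 days.
- Endoscopy on Day -7: from 3 + 7 = 10 to 3 + 8 + 1 = 12 days.

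A 12-day screening covers every schedule, against 28 permitted. A six-day screening never works, since its best case is -4 - (-6) = 2. Seven is therefore the smallest floor at which three days are possible at all.

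**If the window counts back from Day 1.** Endoscopy is no later than Day -4, so Days -3, -2 and -1 always follow it. That gives three diary days in every schedule, even if the preparation and endoscopy days are left out. Seven days are then enough.

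**Which window applies?** SAP 6.1.1 opens with the EoT remission rate and gives the three-day rule as part of defining it. Its wording is not expressly limited to EoT, but nothing visible extends it to screening. SAP 7.2 says the baseline variables are defined in SAP Section 2, which is redacted. The assessment schedule (Protocol Table 8-1) is not in the available text. The visible documents therefore do not establish that the pre-preparation window governs screening.

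**The case for a change.** The strongest case for a change is that the floor is justified in writing by diary collection and ought to secure it. SAP 6.1.1 speaks of the subscores in general, and it is the only rule a reader can find. Even on the most favourable assumptions about preparation and first entry, three of the four permitted endoscopy days fail at seven days. Restating the minimum would cost a few words and no extra visit.

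The arithmetic in this argument stands, and so does the observation that the visible text names no baseline diary window. Two of its steps do not hold. It treats a rule written for the EoT variable as the screening rule. It also supposes that sites would have to invent their own window, although the protocol twice refers them to the Site Operations Manual for Mayo scoring. Replacing the floor with a pre-preparation count could impose a window that the manual does not use.

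A minimum also does not promise that every patient can finish screening in that time. Where more diary days are needed, screening may run longer. Protocol Section 3 requires eligibility to be confirmed before randomization, and Section 5 excludes anyone who deviates from an entry criterion. A patient without a valid subscore should therefore have screening extended rather than be randomized.

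**Conclusion.** No change to the plan follows. The visible text leaves the baseline diary window unstated, and sites and analysts can fill that gap from the Site Operations Manual and the baseline definitions. Under one reading the 7-day floor suffices in every schedule. Under the other it is the best-case minimum, met in 1 of 14 feasible schedules, and up to 12 - 7 = 5 further days within the permitted 28 resolve it.

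The exposure is limited to short screenings, whose frequency the documents do not give, and to eligibility, change-from-baseline summaries and the baseline covariate. Remission at EoT is an absolute threshold on the EoT Mayo score, so the outcome itself does not depend on the baseline diary.

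The conclusion rests on the stated assumptions about preparation day, first entry and day numbering. It also rests on the manual or the redacted text setting one common baseline window, which cannot be verified here.
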